**Table 1: Timing of PENFS vs Sham Interventions, Questionnaires, and HRV**

	Daily	Baseline	Screening (Visit 1)	End of Week 1 (Visit 2)	End of Week 2 (Visit 3)	End of Week 3 (Visit 4)	End of Week 4	8-week follow up
Consent + Enrollment		X						
History		X						
Daily Worst Abdominal Pain (via Smart Watch)	X	X (daily for 1 week)		X (daily during week 1)	X (daily during week 2)	X (daily during week 3)	X (daily during week 4)	
Daily BSFS		X (daily for 1 week)					X (daily during week 4)	
Physical			X					
PENFS vs Sham Device Placement			X	X	X	X		
Rome IV		X						
Bowel Symptom Questionnaire (BSQ)			X					
UCLA CNSR Participant Demographics			X					
IBS-SSS		X	X	X	X	X	X	X
PROMIS Questionnaires			X	X	X	X	X	X
IBS-QOL			X				X	X
HAD			X					
VSI			X				X	
Heart Rate Variability			X	X	X	X		

### **8. Data Collection and Monitoring**

Demographic data and medical history information including co-morbid illness and medication history will be collected and recorded on password protected Excel documents. Questionnaire data collected at different visits will also be stored on password protected Excel documents. We will also monitor for and document any adverse events that occur during this trial. Patients will be given a phone number to call if any questions, concerns, or symptoms related to the device occur.

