***Secondary Aims:***

To compare the efficacy of PENFS therapy versus sham therapy on:

1. the change in mean IBS-SSS at week 8 compared to baseline.
2. the proportion of adult patients with IBS who experience at least a 50-point reduction on the IBS-SSS after 4 weeks of treatment and at the extended follow up period at week 8. These patients are considered clinical responders.
3. the proportion of adult patients with IBS who experience an improvement of  $\geq 30\%$  from baseline in weekly average of the daily worst abdominal pain scores after 4 weeks of treatment. These participants are considered a responder.
4. the change in mean weekly average of the daily worst abdominal pain scores after 4 weeks compared to baseline in adult patients with IBS.
5. the change in average weekly abdominal pain symptoms after 4 weeks of treatment and at extended follow-up (8 weeks) compared to baseline, assessed through the PROMIS Gastrointestinal Belly Pain Scale.
6. the change in average daily stool consistency after 4 weeks of treatment compared to baseline, assessed using the Bristol Stool Form Scale (BSFS).
7. the change in average weekly bowel habits after 4 weeks of treatment and at extended follow-up (8 weeks) compared to baseline, assessed through the PROMIS Gastrointestinal Constipation Scale and Gastrointestinal Diarrhea Scale.
8. the change in average weekly bloating symptoms after 4 weeks of treatment and at extended follow-up (8 weeks) compared to baseline, assessed through the PROMIS Gastrointestinal Gas and Bloating Scale.
9. the change in IBS-QOL in adult patients with IBS after 4 weeks of treatment and at extended follow-up (8 weeks) compared to baseline.
10. the change in resting cardio-autonomic tone, i.e. HRV, over 4 weeks of treatment compared to baseline.
11. the safety and tolerability of PENFS therapy versus sham therapy in adult patients with IBS.

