##### **6. Technology**

The IB-Stim/PENFS device consists of a battery activated generator and wire harness that connects to the generator. Four leads are also attached to the generator, each with a sterile 2 mm, titanium needle. Prior to device placement, the patient's ear is cleaned with alcohol wipes and the ear is trans-illuminated to identify neurovascular bundles that are avoided during needle placement. The generator is attached with adhesive to the skin behind the patient's ear, just above the mastoid process. Each of the 2 mm needles are inserted into the dorsal and ventral aspects of the ear, within 1-1.5 mm of the visualized vascular branches to create a field effect. The PENFS device settings are standardized and deliver 3.2 volts with alternating frequencies (1 ms pulses of 1 Hz and 10 Hz) every 2 s. This stimulation targets central pain pathways through branches of cranial nerves V, VII, IX, and X, which innervate the external ear. The PENFS device generator has a battery life of 5 days and delivers stimulations in 2-hour cycles. Patients remove the device at home on day 6 of treatment. Original protocol from Kovacic et al.

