### ***Assessments and Questionnaires:***

Administration of questionnaires throughout the study is shown in Table 1 and Figure 2.

Patients will provide telephone consent for enrollment into the study. During the this phone call, the investigator will obtain the participant's medical and medication history to check eligibility. After enrollment, patients will complete an online daily questionnaire to assess daily stool consistency (7-point Bristol Stool Form Scale [BSFS]) and a daily question pertaining to daily worst abdominal pain (measured using an 11-point scale) that will be delivered by the smart watch, for one week prior to device placement. If patients do not elect to use the SmartWatch, then they will complete the daily question pertaining to daily worst abdominal pain via an online questionnaire. The questionnaires will provide a baseline for daily worst abdominal pain and stool consistency. In order to be enrolled into the study, patients must have an average daily worst abdominal pain score between 4 and 8, have a minimum of 2 days per week of abdominal pain, and have completed at least 4 out of 7 of the daily worst abdominal pain questionnaires.

If enrollment criteria are met, patients will then present to the UCLA G. Oppenheimer Center for Neurobiology of Stress and Resilience one week after enrollment for their first visit, where they will get a physical examination, complete additional questionnaires, undergo a measurement of HRV, and have the initial PENFS device placed by a trained health care professional (LC, AL, EL). After initial device placement, patients will be instructed to return to UCLA every 7 days (leeway of +/- 2 days in each direction will be allowed) for a total of 4 visits for device replacement and completion of additional questionnaires. Four different devices will be placed in total (at the start of weeks 1, 2, 3, and 4).

Although the IB-Stim device is currently FDA approved for use for 3 consecutive weeks, children in the original study by Kovacic et al actually received 4 consecutive weeks of device treatment. The authors chose to analyze the data after 3 consecutive weeks as children did not return to the clinic after the 4th week of treatment. However, we will analyze IBS symptom severity, abdominal pain, bloating, and bowel habits after the completion of the 4th week of treatment. Again, actual stimulation time is 5 days per week with 2

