### **UCLA budget and costs**

The remaining costs of the personnel, equipment, patient stipends, and statistical support will be provided by the PI and Division of Digestive Diseases. This will include a research coordinator to assist with patient recruitment and coordination for this project. Equipment to measure HRV is also available through the UCLA G. Oppenheimer Center for Neurobiology of Stress and Resilience at no additional cost. Budget is outlined in Table 2.

[figure not shown]
**Human Subject Stipends.** Patient stipend payments include parking. Parking rate at UCLA is \$13 per in-person visit, each subject will have 4 in-person visits (\$52/subject total). Patients will be paid stipends of \$25 per set of questionnaires and we expect each subject to complete 7 sets of questionnaires not including the daily abdominal pain questionnaire (baseline, 4 visits, week 4 follow-up, week 8 follow-up). This equates to \$175/subject, making the total payment per subject to be \$227 with an additional driving compensation if applicable.

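### Aim 11 compares safety and tolerability between arms, but the plan describes no scheduled adverse-event enquiry, defines no tolerability measure, and has no in-person visit after the fourth device

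*Combined protocol and SAP*

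**What the plan says.** Item 11 of the Secondary Aims is to compare "the safety and tolerability of PENFS therapy versus sham therapy in adult patients with IBS". The Statistical Analysis section applies a simple two-sample test to all secondary aims.

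Collection is described in section 8, Data Collection and Monitoring, in two sentences. The first is a general commitment: "We will also monitor for and document any adverse events that occur during this trial". The second gives the route: "Patients will be given a phone number to call if any questions, concerns, or symptoms related to the device occur". Timing, a standard question, grading and an assessor of relatedness are not given.

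On contact, the Assessments and Questionnaires section has patients returning "for a total of 4 visits for device replacement and completion of additional questionnaires", with a new device placed at the start of each of weeks 1 to 4. The budget section agrees: "each subject will have 4 in-person visits". Section 6 (Technology) adds: "Patients remove the device at home on day 6 of treatment". The IBS-SSS and PROMIS text makes the week-4 and week-8 assessments online surveys. Table 1 has no row for adverse events or device removal, and lists the physical examination at visit 1 only.

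**The concern.** A between-arm comparison needs events to be sought in the same way from everyone. Under the plan as written, what is recorded may depend on whether a patient chooses to call and whether he or she links a symptom to the device. A patient's belief about allocation could affect both decisions. The plan recognises that such beliefs exist, since it asks every participant to guess the allocation after 4 weeks. An arm difference could be created or hidden in this way, and its direction cannot be predicted from the documents.

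Tolerability has a further problem. No variable is defined for it, and no record is described of whether a device came off early or why. The budget nevertheless expects 5 dropouts per arm using 2 devices each on average, so early stopping is foreseen.

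The Innovation section says there are no trials of PENFS in adults with IBS. Safety data are therefore a main product of this pilot, and a finding of few side effects would be read with that in mind.

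**Working it through.** **1. Contacts, checked against the plan's own count.** The budget section expects 7 questionnaire sets: baseline, 4 visits, week 4 and week 8.
- 1 + 4 + 1 + 1 = 7.
- 7 x $25 = $175 and 4 x $13 = $52, so $175 + $52 = $227 per subject, as stated.

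**2. Contacts after a device has been worn.** Visit 1 is the first placement. That leaves visits 2, 3 and 4, week 4 and week 8, which is 5 contacts. None is described as including an adverse-event question. The instruments named for them are symptom, quality-of-life and psychological scales, plus HRV at the visits.

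**3. Visits set against devices.** Device 1 is placed at visit 1, device 2 at visit 2, device 3 at visit 3 and device 4 at visit 4.
- Devices 1, 2 and 3 are each followed by a visit (2, 3 and 4): 3 of 4 = 75%.
- Device 4 is followed by none: 1 of 4 = 25%.

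**4. What remains after visit 4.** Scheduled contact is the daily pain and stool diaries in week 4 and the two online surveys. The phone line stays open. Medication use is to be monitored weekly for the whole study, with no mode of contact stated.

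**5. How much a week-4 count could show even if every event were recorded.** The Innovation section reports 6 + 3 + 1 = 10 side effects among 115 children, with no split by arm: 10/115 = 8.7%. Assume that this is the risk per patient over four weeks and that it is spread equally over the weeks.
- With 35 per arm, expected week-4 events = 35 x 0.087 / 4 = 0.76.
- Chance of none = (1 - 0.087/4)^35 = 46%.
- With an assumed four-week risk of 20%, expected events = 35 x 0.20 / 4 = 1.75, and the chance of none = (1 - 0.05)^35 = 17%.

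A clean week 4 would thus be weak evidence under full ascertainment, and weaker if the question had not been put to everyone.

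**6. What cannot be computed.** The documents give no rate at which events would reach the trial by phone or otherwise, so the size of any shortfall has no basis in them.

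**The case against.** The strongest reply is that silence about method does not mean that nothing will be done. Section 8 commits to documenting any adverse event, not only device-related ones, and the phone line also covers questions and concerns. Section 6 has the ear cleaned and trans-illuminated before placement, so it is seen after devices 1 to 3. Table 1 is limited by its title to interventions, questionnaires and HRV. It also omits the weekly medication check, the allocation-guess question and the budgeted pregnancy tests, so a missing row there proves little. Of the 10 earlier reports, 9 were ear discomfort or adhesive allergy, which patients readily link to an ear device. The one syncope was attributed to needle phobia, and placements take place at the clinic. All of this stands, and it limits the point to a risk.

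Four stronger readings are tempting, and the documents do not support them.
- *Staff will not ask about events.* The plan does not say so. It only fails to say that they will.
- *A large share of events will be lost.* This needs a capture rate that is not given. If weeks 1 to 3 were fully captured and week 4 only at an assumed 50% or 25%, overall capture would be (3 + 0.5)/4 = 88% or (3 + 0.25)/4 = 81%. For a 5% event in 40 patients, the chance of seeing at least one would fall from 1 - 0.95^40 = 87% to about 83% or 81%. Full capture in weeks 1 to 3 is itself an assumption.
- *Week 4 alone lies outside the approval.* The plan gives the approval as 3 consecutive weeks and as ages 11 to 18, and the trial enrols ages 18 to 60. Only the duration point is specific to week 4.
- *The plan copies a flaw of the paediatric trial.* The protocol mentions the missing clinic return there to explain why that trial was analysed at 3 weeks. Here outcomes are collected online after week 4.

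What survives is that nothing in the text tells staff to ask, or tells the analyst what aim 11 measures.

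**Conclusion.** The point holds as a risk to ascertainment together with an undefined outcome. Aim 11 is to be compared between arms, yet no scheduled adverse-event enquiry is described and no tolerability measure is defined. The only named route is a call that the patient starts. The exposure is greatest for device 4, the 1 of 4 device-weeks with no visit after it, where following the text as written leaves events to spontaneous report. No number can be put on the loss.

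This rests on the visible text. The timeline figure is not shown in the copy reviewed, and if it schedules a safety question the point narrows accordingly. It does not put the efficacy aims in doubt. It is a cheap improvement, best made before data collection because events not asked about at the time may not be recoverable later.

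**What to change.** Add an adverse-event row to Table 1. Ask every participant the same short set of questions at visits 2 to 4 and in the existing week-4 and week-8 online surveys:
- any new or worse symptom, whether or not thought related to the device;
- ear pain, skin reaction, bleeding and fainting;
- date of device removal and the reason for it.

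Have a masked investigator record relatedness. Define aim 11 as the proportion with any event and the proportion with early device removal, each by arm. State the denominator for both, because the Statistical Analysis section excludes patients with less than one full week of data and defines no separate safety set. Keep the phone line for use between contacts.

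The cost is a few extra questions at contacts that already exist and one table row, with no new visit. More minor events will be reported in both arms. The online questions will not let anyone see the ear after device 4, but they do ensure that every participant is asked.

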### Secure Data Analytics For SmartWatches:

As is the case in IRB #16-000166, data collected from the SmartWatch sensors and radio frequency beacons will be encrypted and transmitted through secure socket protocol (SSL). The SSL guarantees encryption and secure data transmission from patient's home or rehab center to the server. Servers hosting the data are HIPAA compliant machines located on UCLA campus.

## 9. Statistical Considerations

### Sample Size Calculation

Power calculations determined that at least 22 patients would be needed in each arm in order to achieve 95% power to detect at least a 30% reduction in worst daily abdominal pain scores. This power calculation was based on a study by Krasaelap et al, which evaluated the efficacy of PENFS on at least a 30% reduction of worst abdominal pain severity in adolescents with IBS.

We will aim for a sample size that will surpass the number needed to achieve at least 95% power, with a goal of 35 patients in each arm. We will also aim to enroll an additional 5 patients in each arm to account for potential dropouts or losses to follow-up. We will perform an interim analysis about one year after study enrollment has started or when each group has achieved completion of 22 subjects, whichever occurs first (will compare group data but not break the code). An estimate of the study profile is presented in Figure 1.

[figure not shown]

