## 7. Study Protocol

### ***Randomization and Masking:***

Patients who meet study eligibility criteria will be randomly assigned (1:1) in blocks of two and four, using a code generated by a randomization program to 4 weeks of stimulation with an active or inactive (sham) PENFS device. Allocation will be concealed, and all physicians, statisticians, participants, and research coordinators will be unaware of device codes. One research coordinator who has no patient contact (CL) will be unblinded and handle allocation and storage of devices.

The sham devices will be identical to the active devices but will not administer electrical charges. Per manufacturer design and patient anecdotal experience from previous studies, both active stimulation and sham are below detectable sensation threshold. Per report from previous studies, some patients may experience a sensation around the ear after percutaneous needle placement; however, this sensation can occur with equal likelihood in the active or sham device. All subjects will be asked if they believe they were randomized to the active PENFS therapy arm or the sham therapy arm at the end of 4 weeks of treatment, and these results will be analyzed.

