### **Heart Rate Variability (HRV)**

HRV will be assessed at baseline/visit 1 and at the end of weeks 1, 2, and 3 (visits 2, 3, and 4 respectively) of treatment, with the goal to determine if HRV (cardio-autonomic tone) changes over 4 weeks of PENFS treatment vs. sham treatment and if HRV predicts response to PENFS. The previous protocols used for HRV analysis have previously been published by members of our research group and are summarized below. HRV will be recorded for 5-minute intervals using a 2-lead electrocardiogram (ECG) attached to patients' upper chest. ECG data will be collected using the BioPac recording system (MP100A-CE; BioPac Inc., Santa Barbara, CA, USA) and will be manually screened for artifacts. The AcqKnowledge peak detection algorithm (V3.8.2; BioPac, Inc.) will be used to determine intervals between adjacent QRS complexes. The interbeat (R-R) interval data will be used for HRV analysis (Kubios HRV 2.0, Biosignal Analysis and Medical Imaging Group, Dept. of Physics, University of Kuopio, Finland). Autoregression (AR) frequency analysis and Fast Fourier transform (FFT) analysis were performed on one continuous 2-minute segment (epoch) of data to avoid inclusion of artifacts, which can distort HRV data. The AR and FFT analyses should yield measures of HF power in normalized power based on a frequency band of 0.15-0.4 Hz and the LF/HF ratio with LF power defined as the interval between 0.04 and 0.15 Hz. A model order of 16 will be used in the AR analysis with no spectral factorization. FFT analysis will use Welch's periodogram method with a window width of 256 s and window overlap of 50%.

The timing of device placements, questionnaires, and HRV assessment is further outlined in Table 1 and Figure 2.

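### The interim compares coded groups with an unbroken code as its only safeguard, and if the treatment works as the plan assumes, the comparison itself will probably show which group is PENFS

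*Combined protocol and SAP*

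**What the plan says.** Section 9 (Statistical Considerations, Sample Size Calculation) states: "We will perform an interim analysis about one year after study enrollment has started or when each group has achieved completion of 22 subjects". The sentence ends with "completion of 22 subjects, whichever occurs first (will compare group data but not break the code"), so group data will be compared while the code stays sealed. The same section ties this number to the power statement for worst daily abdominal pain: "at least 22 patients would be needed in each arm in order to achieve 95% power". The recruitment goal is 35 per arm plus 5 per arm for dropouts.

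Section 7 (Randomization and Masking) says that "all physicians, statisticians, participants, and research coordinators will be unaware of device codes". The one exception is a coordinator without patient contact, who "will be unblinded and handle allocation and storage of devices"; no interim task is given to that role.

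The documents do not say who makes the interim comparison, on which endpoint, who sees it, or what follows from it. No independent statistician or monitoring committee is named.

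**The concern.** A sealed code protects masking only if the results do not point to the active arm. Here the groups are to be compared at the sample size that the plan regards as nearly certain to show a difference. If it does, the direction of the difference names the arm and the seal no longer protects much.

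Two things could then be handled by people who have inferred the arm:

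- **Analysis choices.** The Statistical Analysis section leaves several open: t-test or Mann-Whitney according to normality, the details of the mixed model for IBS-SSS, and how the rule excluding patients with less than a full week of data is applied.
- **HRV processing.** One secondary aim is "the change in resting cardio-autonomic tone, i.e. HRV, over 4 weeks of treatment compared to baseline". This outcome is not self-reported. The ECG data "will be manually screened for artifacts", and the spectral analysis uses "one continuous 2-minute segment (epoch) of data to avoid inclusion of artifacts". Both steps involve judgement. A two-group comparison needs a group label for each participant included, so whoever runs it can place those participants in coded groups.

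**Working it through.** **Inputs.** From Sample Size Calculation: 22 per arm, 95% power, worst daily pain. From Randomization and Masking: 1:1 allocation. Alpha is not stated; two-sided 0.05 is assumed and varied below.

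**The plan's own figure.** The 22 per arm cannot be reproduced forwards, because no responder rates, SD or alpha are given. Solving backwards, the implied standardised difference is 3.605 × √(2/22) = 1.09, and 2 × (3.605/1.09)² = 21.9, which rounds up to 22. For responder rates, pairs such as 30% against 81% fit. This shows consistency, not reproduction. The missing inputs are not needed below, since power and alpha together fix the expected test statistic.

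**Step 1: expected test statistic at 22 per arm.** 1.960 + 1.645 = 3.605.

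**Step 2: probability that the better-scoring group is PENFS.** Φ(3.605) = 0.99984, or 99.98%.

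**Step 3: sensitivity to alpha.** With two-sided 0.10, Φ(3.290) = 99.95%. With two-sided 0.01, Φ(4.221) is above 99.99%.

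**Step 4: responder-rate version.** For sham rates of 10% to 40%, with the PENFS rate solved for 95% power at 22 per arm, exact binomial sums give 99.98% with the normal-approximation test and above 99.99% with Fisher's test.

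**Step 5: an earlier look.** The one-year trigger may come first; no accrual rate is given, so these sizes are illustrative. Φ(3.605 × √(n/22)) gives:

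| n per arm | Probability |
|---|---|
| 15 | 99.9% |
| 10 | 99.2% |
| 5 | 95.7% |

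**Step 6: smaller true effects at 22 per arm.** Φ(3.605 × fraction of the design effect) gives:

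| Fraction | Probability |
|---|---|
| 0.75 | 99.7% |
| 0.50 | 96.4% |
| 0.25 | 81.6% |
| 0 | 50% |

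**Step 7: IBS-SSS.** The documents give no effect size, so these are assumptions. Φ(d × √(22/2)) is 84% for d = 0.3, 95% for d = 0.5 and 99.6% for d = 0.8.

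**The case against.** **The code stays sealed.** The masking section asks only that staff not know the device codes. That is correct. A reader might infer that the interim breaches this section, but its literal requirement is still met. What is weakened is its purpose.

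**99.98% is not what an observer knows.** It is the chance that the direction is right, given a very large effect on worst pain, which is not the primary endpoint. With even prior odds of that effect and of none, direction alone is right 0.5 × 0.9998 + 0.5 × 0.5 = 75% of the time. This stands, and the figure must be read as conditional. An observer also sees the size of the gap, however. Under the same even odds, a significant result occurs in 0.5 × 0.95 + 0.5 × 0.05 = 50% of looks at 22 per arm, and in those the better group is PENFS with probability (0.475 + 0.0125)/0.50 = 97.5%. At 10 per arm a significant result is less likely: 68% under the design effect, against 95% at 22.

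**Later participants.** A reader might count the 70 − 44 = 26 planned completers still to come at 22 per arm, and their 26 × 4 = 104 HRV recordings, as exposed. The documents do not support that. Labels are needed only for participants in the interim dataset, allocation is concealed, and nothing says later devices or records carry a visible group label.

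**The link to HRV.** A reader might assume that the interim analyst also screens the ECGs. The documents do not say who does either task, or when screening takes place. The HRV route is possible, not shown.

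**The meaning of group data.** If only recruitment or retention is meant, the point falls away. Calling the look an interim analysis, timing it at the powered sample size and adding a caveat about the code all suggest outcome data, but the text should say.

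**Conclusion.** The concern holds in a limited form. The plan's one stated safeguard does not reliably keep the active arm hidden from anyone who sees the coded comparison. The chance that the better group is PENFS is 99.98% at 22 per arm if the design effect on worst pain is true, 96% with half that effect and 50% with none. For IBS-SSS only an assumed range, 84% to 99.6%, can be given. These figures rest on two-sided alpha of 0.05, but the first hardly changes between 0.01 and 0.10.

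The exposure covers those who see the result, the analysis choices still open, and any HRV recordings from participants in the interim dataset that have not yet been hand-screened. Participants stay masked. A reader might also infer inflated type I error from the unplanned boundary; the plan provides for no early claim or stop, so that does not follow. The case for change is that masking is put at risk for a look to which no decision is attached. It should be corrected, but it does not invalidate the primary analysis.

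**What to change.** In Sample Size Calculation, restrict the interim to data pooled across arms: recruitment, retention, and a single SD of IBS-SSS change computed over all participants without group labels. State that outcomes will not be compared by coded group before database lock, and that no efficacy claim, trial stop or design change follows from the look. In the HRV section, state that artifact screening and epoch selection are done on recordings that carry no group label.

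This takes a few sentences of text and recordings filed without labels. Sample size, alpha, power and the final test are unchanged. The team gives up an early view of the group difference, for which the plan has no stated use.
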